### Study Procedures/Activities

A woman scheduled to undergo urogynecologic surgery will be informed by her surgeon she is eligible for study enrollment at her standard-of-care pre-operative appointment. At that time, if the patient wishes, written informed consent will be obtained and the patient will be assigned a study identification (ID) number. On the day of surgery, the patient will meet with her surgeon briefly again in the pre-operative area to confirmed continued design to participate in the study and to review the surgical plan. Premenopausal subjects (i.e. last menstrual period less than 1 year ago) who have not previously undergone hysterectomy undergo a urine pregnancy test as part of their standard clinical care to assure non-pregnant status on day of surgery. The results of this test will be utilized to determine final study eligibility, i.e. those who are determined to be pregnant will be excluded from the study. Regardless of study group assignment, the subject will receive pre-operative intravenous prophylactic antibiotics, which is the standard of care per hospital policy. Once the subject is in the operating room and has undergone induction of anesthesia and placement of a transurethral catheter for clinical care, a urine sample will then be obtained at the start of the case. A vaginal swab will also be obtained. The process of obtaining these samples will take less than 1 minute and will not significantly prolong anesthesia time. These samples will be saved for microbiome analysis. The planned surgery will then be performed. Then, while still under general anesthesia and during the final safety cystoscopy performed for the subject's standard clinical care, if the patient has not had any intraoperative events that exclude her from the study, the surgeon will open the patient's randomization envelop to determine study arm assignment (to gentamicin or no instillation group). After a final foley catheter is placed, for the subject's standard clinical care, another urine sample for microbiome analysis will be obtained, as will a vaginal swab for vaginal microbiome analysis. Then, if the patient is randomized to gentamicin, 80mg of gentamicin in 50 mL of normal saline will be infused into the patient's bladder through the standard-of-care transurethral catheter by the surgeon. The surgeon will then clamp the catheter and label the catheter with the clamping time. If the patient is randomized to no instillation, the surgeon will clamp the catheter and label the catheter with the clamping time. The purpose of clamping the catheter for subjects receiving usual care will be to ensure patients are blinded if they wake up and notice their catheter. The subject will then proceed

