
as usual to the postoperative anesthesia care unit (PACU), with instructions for the PACU nurse to unclamp the catheter 1 hour after the clamping time. All patients will then receive usual postoperative care including an active voiding trial as indicated. During the voiding trial, which is performed as part of the subject's standard clinical care, the transurethral catheter is disconnected from the collection bag. Then the subject's bladder is backfilled with approximately 300 mL of sterile water or saline. The catheter is then removed and the patient is instructed to urinate. The voided volume is measured. The post-void residual is also measured non-invasively by bladder scan.

After surgery, as is part of routine care, the patients will call the surgeon's office if they have UTI symptoms and these calls will be addressed in the usual fashion by the nursing and physician office staff. The patients will give catheterized urine samples as indicated for UTI symptoms which will be processed at a UCSD laboratory.

At 6 weeks after surgery the patient will be seen for a standard-of-care postoperative appointment. At this time, the patient will undergo some standard-of-care health questions related to post-operative healing and any adverse health events since surgery. For the specific purposes of the study and at the FDA's recommendation, all patients at the 6 week post-operative visit will be asked whether they have experienced new onset of hearing loss, tinnitus, dizziness, or vertigo since surgery. For the purposes of the study, if the patient does not come to their post-operative appointment, they will be called at to see whether they have been treated for UTI or have UTI symptoms since surgery. They will also be asked about any other adverse health events since surgery.

Visit	Timing	Purpose	Location	Time Required	Testing
1	Within 4 weeks of surgery	Standard-of-care preoperative counseling, study recruitment and informed consent process	WPMC	60 minutes	Standard-of- care complete blood count, serum electrolytes, serum creatinine and blood urine nitrogen, pregnancy test for women of childbearing potential, and urinalysis and/or urine culture for all patients

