#### Data Analysis/Interpretation

Subjects' data will be analyzed "as treated". Preoperative and perioperative variables will be summarized by means with standard deviations for continuous variables and rates and proportions for categorical variables. To determine whether any significant baseline differences exist between the study arms, preoperative and perioperative variables of the two study arms will be compared using chi-square test for categorical variables or Student t-test or Wilcoxon rank sum test for continuous variables.

The primary outcome of the study, proportion of patients who are clinically treated for UTI, will be analyzed with a chi-squared test. All adverse events will be listed with description of type and severity. The proportion of patients with each type of postoperative adverse event (diarrhea, yeast infection, hospital admission with organ dysfunction, and death) in each arm will also be compared using a chi-squared test. Statistical significance will be defined as  $\alpha$ <0.05.

In order to perform our sample size calculation, we first wanted to baseline postoperative UTI rates according to the definition of our primary outcome at our institution. Chart queries were performed for all GIVE-IT candidates during 2-month time period (Jan-Feb 2019; N=41) at Kaiser San Diego (our FPMRS fellowship sister institution), as it is currently our practice at UCSD (but *not* at Kaiser) to prescribe oral antibiotic prophylaxis following SUI surgery, which could alter UTI rate. The UTI rate in this chart query was 17%. To detect a meaningful reduction in UTI from 17% in controls to 8% in intervention group ( $\alpha = 0.05$ , one-tailed) with 80% power ( $\beta = 0.2$ ), 166 subjects will be needed per arm. This effect of 50% reduction as a meaningful outcome is derived from the similar effect of oral antibiotic post-operative UTI prophylaxis seen in a similar clinical trial. Accounting for 20% dropout or loss to follow-up, we will recruit 200 subjects per arm. Our benchmark for successful recruitment will be approximately 50% recruitment completed 6 months after the first subject is enrolled. In order to complete enrollment more rapidly, we anticipate adding Kaiser San Diego as a secondary study site.

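### Minor, wrong as written: 200 per arm covers 17% loss, not the stated 20%; at 20% loss 160 per arm remain against the 166 required

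*Combined protocol and SAP*

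**What the plan says.** All the figures are in the sample-size paragraph of section 9, Data Analysis/Interpretation. The target is a fall in treated UTI from 17% to 8%, at alpha 0.05, "one-tailed) with 80% power". From this the plan concludes that "166 subjects will be needed per arm". The allowance for loss follows: "Accounting for 20% dropout or loss to follow-up, we will recruit 200 subjects per arm". No inflation formula is given, and no other section offers a different rule.

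Three other statements bear on the point:

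- **Primary test.** The same section says: "The primary outcome of the study, proportion of patients who are clinically treated for UTI, will be analyzed with a chi-squared test". It does not say how a one-tailed level would be applied to that test.
- **Control rate.** The 17% comes from a small chart review: "Chart queries were performed for all GIVE-IT candidates during 2-month time period (Jan-Feb 2019; N=41".
- **Follow-up.** Under Study Procedures/Activities, "if the patient does not come to their post-operative appointment, they will be called" to ask about UTI treatment and symptoms. Data Collection adds a final review of the medical record to resolve missing data.

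**The concern.** An allowance for loss is a claim about how many of those recruited can be lost before the analysis falls below its required size. Here the requirement (166), the allowance (20%) and the recruitment figure (200) cannot all be true. The usual cause is adding 20% of the target to the target, when the target should be divided by the fraction expected to remain.

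What is at stake is a stated property of the design. Someone monitoring follow-up would take 20% as the point below which the planned size is safe. On the plan's own figures that point is 17%, and loss between 17% and 20% leaves fewer women than the plan says it needs.

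**Working it through.** **Inputs**, all from Data Analysis/Interpretation: p1 = 0.17, p2 = 0.08, one-tailed alpha 0.05 (z = 1.645), power 80% (z = 0.842), 166 required per arm, 20% loss, 200 recruited per arm.

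**1. Reproduce the 166.** Pooled normal formula, no continuity correction:

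n = [z_α √(2p̄(1−p̄)) + z_β √(p1(1−p1) + p2(1−p2))]² / (p1−p2)²

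- p̄ = 0.125, so √(2 × 0.125 × 0.875) = 0.4677
- √(0.17 × 0.83 + 0.08 × 0.92) = √0.2147 = 0.4634
- n = (1.645 × 0.4677 + 0.842 × 0.4634)² / 0.09² = 1.3439 / 0.0081 = 165.9, so 166

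The plan's figure is confirmed on its stated inputs.

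**2. Check the allowance.**

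| Quantity | Calculation | Result |
|---|---|---|
| Remaining per arm at 20% loss | 200 × 0.8 | 160 |
| Shortfall | 166 − 160 | 6 per arm, 12 in total |
| Largest loss that 200 absorbs | 1 − 166/200 | 17.0% |
| Recruitment that covers 20% | 166 / 0.8 = 207.5 | 208 per arm |
| Likely source of the 200 | 166 × 1.2 = 199.2 | 200 |

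The last row is an inference.

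**3. Size the effect.** Power = Φ{[(p1−p2)√n − z_α √(2p̄(1−p̄))] / √(p1(1−p1) + p2(1−p2))}. At n = 160, one-tailed: (0.09 × 12.649 − 0.7693) / 0.4634 = 0.797, and Φ(0.797) = 78.7%. The same formula gives:

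| Loss from 200 | Evaluable per arm | One-tailed 0.05 | Two-sided 0.05 |
|---|---|---|---|
| 10% | 180 | 82.8% | 73.5% |
| 17% | 166 | 80.0% | 70.0% |
| 20% | 160 | 78.7% | 68.4% |
| 25% | 150 | 76.4% | 65.6% |

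The slip costs 80.0 − 78.7 = 1.3 points one-tailed, or 70.0 − 68.4 = 1.6 points two-sided.

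**4. Compare with the uncertainty in the control rate.** Keep the ratio 8/17 and 166 per arm, and move the control rate by one point. One-tailed power becomes 77.5% at a control rate of 16% and 82.3% at 18%. A one-point error in a rate taken from 41 charts therefore matters more than this slip.

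**The case against.** The strongest objection is that the practical effect is close to nil and that 78.7% depends on the formula. At 160 per arm, one-tailed, an unpooled formula gives 79.2%, the arcsine formula 79.6%, and exact binomial enumeration of the uncorrected pooled z test 79.8%. On the exact calculation 166 gives 81.2%, so 160 very nearly delivers the planned 80%. This stands as a caution about the absolute figure. It does not rescue the sentence: the exact drop is 81.2 − 79.8 = 1.4 points, about the same as before, and 160 is still below the plan's own requirement of 166.

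A second objection is that loss above 17% may be rare, given the phone call for missed visits and the final record review. That is fair, but the documents give no observed loss rate, and both measures act only after surgery. Consent comes at the pre-operative visit ("written informed consent will be obtained and the patient will be assigned a study identification (ID) number"). The envelope is opened at the final cystoscopy, and only "if the patient has not had any intraoperative events that exclude her from the study". If the 200 counts consented women, losses before randomisation also use up the allowance. A count per arm more naturally means randomised women, so this is a request for clarity. The mismatch is the same on either reading.

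A third objection is that simply replacing 20% by 17% would fit the assumption to the recruitment figure and hide the shortfall. That is a good reason to state both figures.

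**Conclusion.** The statement is wrong as written, and the error is minor. On the plan's own requirement of 166, recruiting 200 per arm allows for 17% loss. At 20% loss the trial is 6 per arm short, and one-tailed power is about 1.3 points lower by the pooled formula (78.7% against 80.0%). The arithmetic on the allowance needs no assumption beyond the plan's own numbers.

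The power figures rest on true rates of 17% and 8%, equal loss in the two arms, and a chi-squared test run one-tailed at 0.05. The analysis text does not confirm the last of these. A two-sided test would cost about 10 points at 166 per arm (80.0% to 70.0%), which is a separate and larger matter than this one.

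**What to change.** Restate the allowance and leave recruitment at 200 per arm. Suggested wording: *Recruiting 200 per arm allows for up to 17% loss while keeping 166 evaluable per arm; at 20% loss, 160 per arm would be evaluable.* If 20% is not the loss actually expected, changing that one figure to 17% is enough. Say also whether the 200 counts women consented or women randomised.

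A power clause is optional: *giving 78.7% power for 17% versus 8% at one-tailed alpha 0.05 (pooled normal approximation, no continuity correction)*. Add it only once the primary test is stated to be one-tailed. If the test is two-sided, the corresponding figure is 68.4%.

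The cost is one figure or one sentence, and the stated allowance becomes slightly less favourable. Raising recruitment to 208 per arm (2 × 208 − 400 = 16 more women) would also make the 20% true, but it would recover only 1.3 points and is not proposed.
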